## 1. SUMMARY OF THE STUDY

TITLE	Retrospective Observational Cohort Study SYMBOL CUP 2
SHORT TITLE	SYMCOR-2
INVESTIGATOR	[name] [name]
SPONSOR	DEDIENNE SANTE S.A.S.
JUSTIFICATION / CONTEXT	Documentation of the clinical efficacy and safety of SYMBOL CUP DMR HA and SYMBOL CUP DM CEM dual mobility acetabular implants.
METHODOLOGY	Retrospective observational cohort study
MAIN OBJECTIVE	Estimate the safety of these implants under normal conditions of use
PRIMARY ENDPOINT	Implant survival rate at 2-year follow-up
SECONDARY OBJECTIVE	Estimate the efficacy of these implants under normal conditions of use
SECONDARY ENDPOINTS	
 
- Safety: Intra and extra-prosthetic dislocation rates
 
- Safety: Incidence of other adverse events
 
- Effectiveness: Harris Hip Score (HHS)
 
- Effectiveness: Devane classification
 
- Effectiveness: Charnley classification
 

INCLUSION CRITERIA	
 
- Any patient operated by [name] who has undergone hip replacement surgery with SYMBOL CUP DMR HA or SYMBOL CUP CEM acetabular implant.
 
- Patient having reach 2-year follow-up on March 01, 2018
 

NON-INCLUSION CRITERIA	
 
- Explicit refusal by the patient to allow data describing his pathology and treatment to be included in this study.
 
- Minor patients or patients under guardianship.
 

RESEARCH PROCESS	
Retrospective collection of clinical data:
 
 
- Recorded in the orthopedic surgery department's patient files, from the patient's pre-surgical assessment to the latest news at 2-year follow-up.
 
- Obtained by telephone interview for data up to 2-year follow-up, if the medical file does not provide all the source information. The telephone interview will be carried out by the investigator (or his secretariat) or by a clinical research associate delegated by the sponsor and approved by the investigator.
 

NUMBER OF SUBJECTS	Minimum total number of subjects: n=20
PLANNED NUMBER OF CENTERS	Single-center, single-investigator study

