**Table 4 : SYMBOL CUP DM CEM: Sales volume in France under this brand**

Year	2014	2015	2016	2017	Provisional 2018
In public healthcare facilities	0	0	0	20	50
In non PHSPH private healthcare facilities	19	172	76	180	360
Total	19	172	76	200	410

The specific data resulting from this study will be used to establish the benefit-risk ratio of SYMBOL CUP DMR HA and SYMBOL CUP DM CEM. This information will enable:

- Update of the clinical evaluation for CE mark renewal purposes.
- An assessment of the product's application for inclusion in the Liste des Produits et Prestation Remboursables under the brand names by the Haute Autorité de Santé.

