## **10. STATISTICAL CONSIDERATIONS**

### **10.1. NUMBER OF SUBJECTS TO BE INCLUDED**

The size of the cohort considered to be the minimum in light of studies carried out by other manufacturers is at least 20 with a follow-up of 2 years.

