### **10.2. DATA ANALYSIS – GENERAL INFORMATION: DESCRIPTIVE APPROACH**

- Descriptive statistics: preoperative, operative, postoperative
- Tabulation of adverse events
- Kaplan-Meier analysis of implant survival
- Comparison tests of preoperative versus 1-year and 2-year postoperative efficacy scores.

Tests will be performed with a two-side alpha risk of 5%. Confidence intervals will be at 95%.

Continuous variables will be tested using Student's t-test. Categorical variables will be tested using Chi-2 test.

No subgroup analysis is planned.

No interim analysis is justified given the strict retrospective nature of the study.

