### **10.3. MAIN ANALYSIS**

Prothesis survival: Kaplan-Meier analysis.

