### **10.4. SECONDARY ANALYSES**

Subgroup analyses: Not applicable

- Descriptive statistics
- Continuous variables: Student's t-test or non-parametric tests in case of a breach of the conditions for applying parametric tests.
- Categorial variables: Chi-2 test.

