## IL EST CONVENU ET ARRETE CE QUI SUIT :

### ARTICLE 1 : Mission

Le Docteur [name] accepte de réaliser, pour le compte de la Société DEDIENNE SANTE, l'activité de suivi post-marché décrite ci-après :

\* Produit(s) concerné(s) : SYMBOL CUP DMR HA et SYMBOL CUP DM CIMENTE

\* Nature des travaux. Recueil des informations objectives et quantifiées relatives à :

- la nature du diagnostic avant pose et l'indication retenue.
- le déroulement de l'intervention et le résultat opératoire obtenu.
- l'adéquation entre les tailles d'instruments et tailles d'implants
- l'évolution postopératoire à 1 an et 2 ans, notamment du positionnement et du comportement de ces implants.

Il est entendu que le Docteur [name] fera son possible pour assurer le suivi clinique de ses malades, afin que les résultats obtenus puissent être confirmés avec un plus grand recul clinique. Les informations seront consignées sur des cahiers d'observation spécifiques définis par la cellule d'évaluation clinique de la Société DEDIENNE SANTE, dont un exemplaire est joint à cette convention.

Cadre de l'étude :

Dans le cadre de la directive 93/42/CEE, il s'agit d'assurer le suivi clinique post-commercialisation d'un dispositif médical marqué CE, afin de vérifier la sécurité et les performances revendiquées pour les dispositifs médicaux. Cette étude va permettre de collecter des données cliniques nécessaires à toute évolution des produits fabriqués par la Société DEDIENNE SANTE.

Ce suivi porte sur 20 dossiers de patients ayant un recul minimum de 2 ans. Les résultats correspondants seront transmis à la Société DEDIENNE SANTE. Il s'agit d'une étude rétrospective observationnelle.

Il est expressément mentionné que l'accomplissement de cette mission ne limite en rien l'indépendance du praticien et n'est assortie d'aucune obligation d'utilisation ou de prescription des produits de la Société DEDIENNE SANTE.

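### No outcome is planned by device, although the two cups differ in fixation and the data are meant to support listing under each brand name

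*Combined protocol and SAP*

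**What the plan says.** Section 10.2 lists descriptive statistics, tabulated adverse events, a Kaplan-Meier analysis and tests of scores over time, and then states "No subgroup analysis is planned". Section 10.4 adds "Subgroup analyses: Not applicable". The whole of Section 10.3 is "Prothesis survival: Kaplan-Meier analysis", with no stratum or device factor.

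The sample size is a single total. The summary gives "Minimum total number of subjects: n=20", and Section 10.1 says the minimum cohort "is at least 20 with a follow-up of 2 years". The contract in Annex 5, Article 1, treats 20 as the number of files: "Ce suivi porte sur 20 dossiers de patients ayant un recul minimum de 2 ans". No number per device appears anywhere.

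Section 2.2 says the data "will be used to establish the benefit-risk ratio of SYMBOL CUP DMR HA and SYMBOL CUP DM CEM". It names two uses: updating the clinical evaluation for CE renewal, and an application for reimbursement listing under the brand names. It also says that the earlier CE evaluation had no data on these particular products and that this study is the first to supply them.

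Annex 2 records implant type for every patient. In Section 10, prosthesis type is mentioned only in 10.5, as a characteristic in the sampling-frame description and not as a basis for reporting outcomes.

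**The concern.** The primary endpoint is removal of the implant, and the two cups are held in place differently. Tables 1 and 2 show press-fit with pegs and a cortical screw and a Ti+HAP coating for DMR HA, and cement with no coating for DM CEM. Section 2.2 gives them different generic reimbursement descriptions: an uncemented reconstruction cup and a cemented standard cup. Device is therefore not an arbitrary subgroup here. It is the product about which a conclusion is wanted.

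If only a combined survival figure is reported, a listing file for either brand name contains no result for that cup, and the combined interval is narrower than the evidence on either cup supports. If by-device reporting is left open, it can also be decided after the results are known.

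The stake is mainly the listing. The CE update may rest in part on range-level evidence, since the earlier evaluation addressed the SYMBOL CUP DM range and one certificate covers both cups.

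**Working it through.** **The plan's own figure.** The total of 20 is justified only by what other manufacturers have done. Section 2.3 makes no hypotheses about adverse-event incidence or endpoint changes, and no event rate, precision target or power is given, so 20 cannot be reproduced by a formula. What can be calculated is what 20 patients would show, combined and by device.

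**Inputs**
- n = 20 in total (Sections 1 and 10.1 as a minimum; Annex 5 as the number of files).
- 95% confidence level (Section 10.2).
- Device split: not in the documents. 10/10 and 15/5 are assumed for illustration.
- Follow-up: assumed complete to 2 years, so that Kaplan-Meier reduces to a simple proportion.
- Interval: exact binomial (Clopper-Pearson), an assumption because the plan names no method.

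**No revisions.** The lower limit is 0.025^(1/n), and the point estimate is 100% throughout.

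| n | Where it arises | 95% lower limit |
|---|---|---|
| 20 | combined | 0.025^(1/20) = 83.2% |
| 15 | larger cup, 15/5 split | 0.025^(1/15) = 78.2% |
| 10 | each cup, 10/10 split | 0.025^(1/10) = 69.2% |
| 5 | smaller cup, 15/5 split | 0.025^(1/5) = 47.8% |

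If 2 of 10 patients per cup have no known 2-year status and only known cases count, the limits are 79.4% combined (n = 16) and 63.1% per cup (n = 8).

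**Two revisions, both in one cup, 10/10 split.** With s survivors out of n, the limits are the 2.5% quantile of Beta(s, n − s + 1) and the 97.5% quantile of Beta(s + 1, n − s).
- Combined: 18/20 = 90% (68.3% to 98.8%).
- Affected cup: 8/10 = 80% (44.4% to 97.5%).
- Other cup: 10/10 = 100% (69.2% to 100%).

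The combined 90% describes neither cup.

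**Chance of seeing any revision.** At an assumed true 2-year revision risk of 5%, the probability of at least one revision is 1 − 0.95^n: 64.2% for n = 20, 40.1% for n = 10 and 22.6% for n = 5. A cup with no revisions in a small group has therefore been shown to be safe only within a wide interval, and that interval needs to be reported.

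**Interval method.** Section 10.2 asks for 95% intervals without saying how the survival interval is formed. This matters more once the groups are small.
- No revisions: the Greenwood standard error is 0. The plain interval is 100% to 100%, and the log-log interval is undefined.
- Two revisions in 10: S = 0.80 and SE = √(0.80 × 0.20 / 10) = 0.1265. The plain interval is 0.80 ± 1.96 × 0.1265, or 55.2% to 104.8%, which passes 100%. The log-log form stays in range, at 40.9% to 94.6%.

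**The case against.** The plan never says outright that the devices are pooled, does not define device as a subgroup and does not forbid tables by device. That the Kaplan-Meier analysis is unstratified is inferred from silence. The objective is worded jointly for both implants, and a combined estimate answers it. The cups share liner, cup metal, size range and certificate, so a range-level figure is legitimate. The documents do not say what evidence the listing body requires. Annex 2 records implant type, adverse events and revision dates, so with about 20 files a problem confined to one cup would be visible in the data. Splitting so few patients may also yield little: at 18/2 with no revisions, the lower limit for the smaller group is 0.025^(1/2) = 15.8%. Finally, the interval-method point applies equally to a pooled analysis.

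Most of this is fair. It justifies keeping the combined figure, confining the concern mainly to the listing and treating the interval method as secondary. It does not remove the gap. Followed as written, the rules produce no result for either cup, and two sentences can be read as excluding one. Whatever the listing body requires, a combined figure is not an estimate for a single product. Wide per-device intervals are no reason to omit them, because they show how little is known about each cup.

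**Conclusion.** The concern holds. No outcome is planned by device, while Section 2.2 wants the benefit-risk of both named cups and listing under their brand names. The combined estimate remains valid as a range-level summary but cannot by itself support a conclusion about either cup.

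As an illustration of size, with no revisions among 20 patients the lower limit falls from 83.2% combined to 69.2% per cup at 10/10, or to 78.2% and 47.8% at 15/5. These figures rest on an assumed split, n = 20, complete follow-up and exact binomial intervals. A larger cohort would narrow all of them. The finding itself rests on the text and not on these assumptions. What is missing is a reporting commitment; the data to support it are already collected.

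**What to change.** Amend Sections 10.2 to 10.4 as follows:
- Present implant survival, dislocation, other adverse events and functional scores descriptively for DMR HA and for DM CEM, using the implant-type variable in Annex 2. Give each device's n and 95% interval, with the combined result alongside as a range-level summary.
- Name a survival interval that remains valid with no or few revisions: Clopper-Pearson if every patient has known 2-year status, or an exact-type Kaplan-Meier limit, such as the beta product confidence procedure, if there is censoring.
- Plan no between-device test. For scale, at 10 against 10 the power is only about 24% even for assumed revision rates of 2% and 20% (normal approximation).
- Tabulate diagnosis and first-intention versus revision surgery by device, from Annex 2, and state that differences between devices may reflect case mix.
- Reword the two subgroup sentences so that they do not rule out this presentation, and base device-specific conclusions only on device-specific estimates.

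The cost is a short paragraph, extra table columns and one named method, with no new data. There are two drawbacks. The per-device intervals will be wide and may support only limited conclusions, because the cohort is no larger. Side-by-side columns may also invite comparison, which is why the case-mix statement is needed.

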### **10.3. MAIN ANALYSIS**

Prothesis survival: Kaplan-Meier analysis.

### **10.4. SECONDARY ANALYSES**

Subgroup analyses: Not applicable

- Descriptive statistics
- Continuous variables: Student's t-test or non-parametric tests in case of a breach of the conditions for applying parametric tests.
- Categorial variables: Chi-2 test.

### **10.5. SAMPLING FRAME**

The sampling frame, i.e. all patients operated by the same surgeon in the same institution, for total hip replacement, between the first and the last date of inclusion of patients in the SYMBOL CUP DMR HA or SYMBOL CUP DM CEM cohort, will be the subject of descriptive statistics.

Analysis will focus on age at date of operation, BMI, type of prosthesis, 1st intention or revision (See Questions relating to the sampling frame Annex 2).

Its characteristics will be compared to those of the cohort.

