### **4.1. DESCRIPTION OF MEASURES TAKEN TO REDUCE AND AVOID BIAS**

Consecutive recruitment with provision of sampling frame data.

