## **5. STUDY FEASABILITY**

The clinical research associate (CRA) delegated by the sponsor will make two or three visits to the investigational center:

- An inclusion visit to confirm the investigator's adherence to the protocol and to define the procedures for extracting and transferring anonymized data from the electronic patient record management system. As this is a single-center study, this visit will take place before the protocol is submitted to the CNIL.
- A visit to extract and transfer anonymized data from patient files, and to call patients to obtain their two-year follow-up data. On this occasion, patients will be informed that they may object to the inclusion of their information in this study. During this visit, the sponsor's clinical research associate will check that the data are consistent with the contents of the patient files. He/she will confirm the completeness of the cohort, with consecutive placement of dual-mobility acetabular implants. An anonymized list of all THA during the recruitment period will be obtained and checked to establish the sampling frame. This visit will take place at the start of the study.
- An additional visit by the CRA, to obtain missing data and resolve discrepancies, will take place if necessary.

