## **6. RÉALISATION PRATIQUE DU PROTOCOLE.**

### **6.1. DÉROULEMENT DES VISITES LIÉES A L'ÉTUDE**

The clinical research associate (CRA) delegated by the sponsor will make two or three visits to the investigational center:

- An inclusion visit to confirm the investigator's adherence to the protocol and to define the procedures for extracting and transferring anonymized data from the electronic patient record management system. As this is a single-center study, this visit will take place before the protocol is submitted to the CNIL.
- A visit to extract and transfer anonymized data from patient files, and to call patients to obtain their two-year follow-up data. On this occasion, patients will be informed that they may object to the inclusion of their information in this study. During this visit, the sponsor's clinical research associate will check that the data are consistent with the contents of the patient files. He/she will confirm the completeness of the cohort, with consecutive placement of dual-mobility acetabular implants. An anonymized list of all THA during the recruitment period will be obtained and checked to establish the sampling frame. This visit will take place at the start of the study.

- An additional visit by the CRA, to obtain missing data and resolve discrepancies, will take place if necessary.

In the event of death reported by the patient's entourage without a date, the surgeon will question the civil registry of the patient's commune of birth to obtain the date and cause of death.

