# **7. ELIGIBILITY CRITERIA**

## **7.1. INCLUSION CRITERIA**

Any patient operated by [name] who has undergone hip replacement surgery with SYMBOL CUP DMR HA or SYMBOL CUP CEM acetabular implant and having reach 2-year follow-up on March 01, 2018.

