**Annex 2: List of study variables**
**DATA FROM THE COHORT SYMBOL CUP DMR HA AND SYMBOL CUP DM CEM**

PREOPERATIVE DEMOGRAPHICS	Order number of the surgery with this type of implant
	Type of implant DMR HA or CEM
	Month/year of birth
	Sex
	Surgeon identification
	Date of preoperative visit
	Height (cm)
	Weight (Kg)
	BMI
	BMI class
	Operated side
	Etiology / diagnosis
	Medication
	Medication - Specify
	Medical history
	Medical history - Specify
	Local surgical history on the affected hip
	Local surgical history on the affected hip - Specify
	Surgeon's comments
PREOPERATIVE DEVANE & CHARNLEY CLASSIFICATIONS	DEVANE
	CHARNLEY
HHS PAIN	Pain
HHS FUNCTIONAL ABILITIES - WALKING	Lameness
	Support
	Walking perimeter
HHS FUNCTIONAL ABILITIES – DAILY LIFE	Socks and shoes
	Stairs
	Sitting position
	Public transport
HHS – MOBILITY	Flexion °
	Extension °
	Abduction °
	Adduction °
	External rotation °

	Internal rotation °
	TOTAL MOBILITY
DEFORMATIONS	LLI (cm)
	Flessum °
	Adductum °
	Internal rotation °
	TOTAL DEFORMATIONS
	TOTAL PREOPERATIVE HHS
SURGICAL INTERVENTION	Date of surgery
	Age at surgery
	Intervention duration (min)
	Surgical approach
	Type of intervention
	Surgeon's comments
	Operative adverse events
ACETABULAR COMPONENTS	Cup walls
	Fragile acetabulum zone
	Cup identification
	Size
	Cement
	Reaming diameter
	Liner
	Femoral head
	Diameter
	Bone graft
	Screw
	Pegs
	Associated surgical procedure
FEMORAL STEM	Stem identification
	Cement
	CCD angle
	Collar
	Broach size
	Stem size
	Neck length
	Bone graft
STABILITY	Stability of the hip
INCIDENTS	Operative adverse events
SURGEON'S COMMENTS – END OF SURGERY	Surgeon's comments
1-year postoperative assessment	Date
	Death

	Reason for death
1-year postoperative assessment	
DEVANE & CHARNLEY	DEVANE
CLASSIFICATIONS	CHARNLEY
HHS PAIN	Pain
HHS FUNCTIONAL ABILITIES - WALKING	Lameness
	Support
	Walking perimeter
HHS FUNCTIONAL ABILITIES – DAILY LIFE	Socks and shoes
	Stairs
	Sitting position
	Public transport
HHS – MOBILITY	Flexion °
	Extension °
	Abduction °
	Adduction °
	External rotation °
	Internal rotation °
	TOTAL MOBILITY
DEFORMATIONS	LLI (cm)
	Flessum °
	Adductum °
	Internal rotation °
	TOTAL DEFORMATIONS
	TOTAL 1-YEAR FU HHS
Adverse events and reason	Adverse events at 1-year FU
	Date of occurrence of the adverse event
	Potential reason
Treatment	Without revision surgery
	Surgical revision without component revision
	Surgical revision with revision of components
	Date of revision surgery
	Adverse event solved Yes/No

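### The sampling-frame window in section 10.5 moves with the included patients, so the frame comparison cannot show eligible recipients left out at either end

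*Combined protocol and SAP*

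**What the plan says.** Section 4.1 names one measure against bias: "Consecutive recruitment with provision of sampling frame data".

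Section 10.5 defines the frame as "all patients operated by the same surgeon in the same institution, for total hip replacement", restricted to the time "between the first and the last date of inclusion of patients in the SYMBOL CUP DMR HA or SYMBOL CUP DM CEM cohort". On content, "Analysis will focus on age at date of operation, BMI, type of prosthesis, 1st intention or revision", and the frame is then compared with the cohort.

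Sections 5 and 6.1 describe how the list is obtained: "An anonymized list of all THA during the recruitment period will be obtained and checked to establish the sampling frame". The recruitment period is not dated there, and the timetable in section 1 gives the inclusion period as not applicable. The same two sections give the CRA a further task: "He/she will confirm the completeness of the cohort, with consecutive placement of dual-mobility acetabular implants".

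Section 7.1 takes any patient of the surgeon with either cup "having reach 2-year follow-up on March 01, 2018". That implies a latest surgery date of about 1 March 2016 and sets no earliest one. Section 7.2 excludes patients who refuse, minors and patients under guardianship. Annex 2 records, for each cohort patient, the "Order number of the surgery with this type of implant".

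**The concern.** A frame helps to show that a series is consecutive when its limits are set independently of who entered the series. Here they are not. If the surgeon's earliest recipients of these cups, or the latest ones before the cut-off, were not included, the window contracts to exclude them. The frame comparison then has no trace of them.

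The documents offer ordinary routes to such an omission: refusal, guardianship, or a stop at a round number. On the last, sections 1 and 10.1 set 20 as a minimum, while Article 1 of the investigator contract in Annex 5 speaks of 20 patient files without calling that a minimum.

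The stake is the credibility of a small series. Section 2.2 describes this as the first clinical evaluation specific to these products, and says that it will feed the CE-mark renewal and a reimbursement application. With about 20 patients, one or two unlisted recipients could matter to the two-year survival estimate.

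**Working it through.** The plan gives no figure to reproduce here: the minimum of 20 is justified by other manufacturers' studies, not by a calculation. The check is therefore mainly of the text, with some arithmetic to set bounds. I read the date of inclusion as the date of surgery.

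**1. The span that eligibility allows**
- Earliest possible start: 9 April 2014, the EC declaration of conformity (section 2.2).
- Latest surgery: two years before 1 March 2018, so about 1 March 2016 (section 7.1).
- Length: 365 days to 9 April 2015, plus 327 days to 1 March 2016, gives 692 days, or 692 / 30.4375 = 22.7 months.

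This is an upper bound, because the surgeon's own first use may be later. Tables 3 and 4 show national sales of only 15 and 19 units in 2014. The window in section 10.5 can be any shorter span within these dates.

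**2. Which item could detect an omitted recipient**

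| Position of the omitted recipient | Frame comparison (10.5) | Order number (Annex 2) | CRA check (5, 6.1) |
|---|---|---|---|
| Before the first included case | No | Yes, if numbering counts every implantation | Possibly; no dates, method or output stated |
| Between included cases | On the list | Yes, on the same condition | Possibly |
| After the last included case | No | No | Possibly; no dates, method or output stated |

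The late end is the least covered. The early end relies on a variable that section 10.5 does not name for the comparison.

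**3. How often an omitted patient falls outside the window (assumed inputs)**

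Assume 20 included patients and k eligible patients omitted at random in order of surgery. An omitted patient is outside the window if he or she comes before all 20 or after all 20.
- For one omitted patient: 2/21 = 9.5%.
- Expected number outside: 2 × 2/21 = 0.19 for k = 2; 5 × 2/21 = 0.48 for k = 5.
- At least one outside, k = 2: 1 − (20/22)(19/21) = 17.7%.
- At least one outside, k = 5: 1 − (20/25)(19/24) = 36.7%.

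If instead the files are cut off at one end, every omitted patient is outside.

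**4. What one or two omitted patients could do to the estimate (assumed inputs)**

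Take 20 included patients with none revised and no censoring, use exact (Clopper-Pearson) 95% intervals, and suppose that each omitted patient was revised.
- None omitted: 20/20 = 100% (83.2 to 100).
- One omitted: 20/21 = 95.2% (76.2 to 99.9).
- Two omitted: 20/22 = 90.9% (70.8 to 98.9).

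Steps 3 and 4 show sensitivity. The values of k and the outcomes are not in the documents, so these figures do not measure the bias in this study.

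**The case against.** The strongest objection is that the plan does not depend on the frame alone. A reader might infer from section 4.1 that the frame is the only check on consecutive selection. It is not: the CRA's completeness task is separate, and its wording is not confined to the frame window. The order number also covers much of the early end. Both points stand. What remains is that the CRA check has no stated dates, method or reported result, and the one list named for that visit covers an undated period.

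A second objection is that section 10.5 mainly compares the cohort with the surgeon's wider hip practice on age, BMI, prosthesis type and primary or revision surgery. A concurrent window is reasonable for that, and losing a little time at either end would hardly change it. This also stands. However, section 4.1 ties the frame to consecutive recruitment, and for that use the window matters.

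Third, section 7.1 includes any patient who meets the criteria, and 20 is a floor with no rule to stop there. If the protocol is followed, only refusal, minority or guardianship at an end would shorten the window. Under random omission, about 90% of omitted patients (1 − 2/21) would still fall inside it. This limits the likely size of the problem without removing it.

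Finally, section 10.5 refers to sampling-frame questions in Annex 2. The annex text available for this review lists only cohort variables, so I draw no conclusion about what those questions ask.

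**Conclusion.** The point holds in a limited form. As section 10.5 is written, the frame comparison cannot show eligible recipients left out before the first or after the last included case. The CRA check and the order number cover this in part, and the late end is the weaker.

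A reader might go further and infer that the series was truncated, or that early failures were missed. The documents support neither. They do not show that any omission occurred, and they give no evidence that failures cluster among a surgeon's first cases; section 2.3 makes no hypothesis about the incidence of adverse events. The size of any effect is unknown. The only firm number is the ceiling of 692 days on the eligible span.

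Importance is minor to moderate. The case for change rests on its low cost and on letting the study show that its series is consecutive.

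**What to change.** In section 10.5, and for the recruitment period in sections 5 and 6.1, set a window that does not depend on inclusion. It should run from the surgeon's first implantation of SYMBOL CUP DMR HA or SYMBOL CUP DM CEM, whether or not that patient is included, to the last surgery date that meets the two-year criterion on 1 March 2018 (about 1 March 2016).

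On the anonymised list, flag each recipient of either cup as included or not included. Report the number not included, with reasons.

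The cost is wording in three sections and possibly a slightly longer version of a list that the CRA already has to obtain.

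### Section 10.5 compares the cohort with a sampling frame that contains it, and the t-test it inherits need not hold 5% if group sizes and spreads differ

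*Combined protocol and SAP*

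**What the plan says.** Section 4.1 gives the measures against bias in one line: "Consecutive recruitment with provision of sampling frame data". Section 10.5 defines the frame as all of the same surgeon's total hip replacement patients in the same institution between the first and last inclusion dates. It states that the frame "will be the subject of descriptive statistics", lists age at operation, BMI, type of prosthesis and first intention or revision, and adds: "Its characteristics will be compared to those of the cohort". It does not name a test and does not remove cohort patients from the frame.

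The test has to be taken from the general rules. Section 10.2 says "Tests will be performed with a two-side alpha risk of 5" per cent and "Continuous variables will be tested using Student's t-test". Section 10.4 repeats this for the secondary analyses, with a fallback: "Student's t-test or non-parametric tests in case of a breach of the conditions for applying parametric tests". Neither section says whether the t-test is the pooled or the unequal-variance form, or how its conditions will be checked.

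On size, section 10.1 says only that the cohort "is at least 20 with a follow-up of 2 years". The investigator contract (Annex 5, Article 1) refers to 20 files: "Ce suivi porte sur 20 dossiers de patients ayant un recul minimum de 2 ans". No frame size and no SD for age or BMI is given.

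**The concern.** An ordinary two-sample t-test rests on two conditions that are in doubt here.

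- **Independence of the groups.** A cohort patient who is also in the frame counts on both sides. The two means are then positively correlated, and the test overstates the variance of their difference.
- **Equal variances.** The pooled test tolerates unequal spread when the groups are of similar size, but not when one is several times larger, because the large group then sets the pooled variance. Section 2.1 describes these cups as chosen for particular indications, so a different spread of age or BMI from the surgeon's other patients is plausible, though not documented.

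What is at stake is how the cohort's representativeness is read. A test that is too conservative can miss a real difference between these patients and the surgeon's other patients. A test that is too liberal can report one that is not there.

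**Working it through.** **Inputs from the documents:** two-sided 5% and Student's t-test (10.2), non-parametric fallback (10.4), cohort minimum 20 (10.1; 20 files in Annex 5), and a frame that includes the cohort's hip replacements (10.5).

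**Assumptions, because the documents give no figure:** frame of 40 to 400 including a cohort of 20; ratio r of cohort SD to non-cohort SD from 0.5 to 2; normal data with equal means.

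**Check against the plan's own figure.** With separate groups of 20 and 200 and equal SDs, the pooled test rejects 5.00% of the time, as stated in 10.2.

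**Step 1: overlap alone, equal SDs.** With n cohort patients inside a frame of N, the true variance of (cohort mean − frame mean) is σ²(1/n − 1/N). The two-sample test assumes σ²(1/n + 1/N). For n = 20 and N = 200:
- assumed: 1/20 + 1/200 = 0.055; true: 1/20 − 1/200 = 0.045
- √(0.055/0.045) = 1.106; the critical value on 218 df is 1.971, and 1.971 × 1.106 = 2.18
- two-sided normal tail beyond 2.18 ≈ 2.9%. Simulation (400,000 sets) gives 2.9%.

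Simulated error rates for other frame sizes, with equal SDs:

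| Cohort in frame | Pooled t |
|---|---|
| 20 in 40 | 0.05% |
| 20 in 100 | 1.5% |
| 20 in 200 | 2.9% |
| 20 in 400 | 3.8% |

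Welch's test on the same overlapping groups gives 3.1% to 3.5% (20 in 200) and 1.6% to 2.5% (20 in 100) over r = 0.5 to 2, so changing the test alone does not restore 5%.

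**Step 2: unequal spread, separate groups of n₁ = 20 and n₂ = 180.** Set the non-cohort SD to 1. The expected pooled variance is (19r² + 179)/198, and the test uses it times (1/20 + 1/180) = 0.0556. The true variance of the difference is r²/20 + 1/180. The critical value on 198 df is 1.972.
- r = 0.67: pooled variance 0.947; assumed variance 0.0526; true variance 0.0280; √(0.0526/0.0280) = 1.371; 1.972 × 1.371 = 2.70; tail ≈ 0.7%.
- r = 1.5: pooled variance 1.120; assumed variance 0.0622; true variance 0.1181; √(0.0622/0.1181) = 0.726; 1.972 × 0.726 = 1.43; tail ≈ 15.2%.

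These hand figures fix the pooled variance at its mean. Averaging over the sampling distribution of the two variances (1,000,000 draws) gives:

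| Separate groups | r = 0.67 | r = 0.8 | r = 1 | r = 1.25 | r = 1.5 |
|---|---|---|---|---|---|
| 20 v 20 | 5.1% | 5.0% | 5.0% | 5.0% | 5.1% |
| 20 v 40 | 2.7% | 3.5% | 5.0% | 6.9% | 8.5% |
| 20 v 80 | 1.4% | 2.6% | 5.0% | 8.6% | 12.2% |
| 20 v 180 | 0.8% | 1.9% | 5.0% | 10.1% | 15.4% |
| 20 v 380 | 0.5% | 1.7% | 5.0% | 10.9% | 17.2% |

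**Step 3: the fallback.** Mann-Whitney at 20 v 180 (20,000 simulated sets) gives 1.7% at r = 0.67, 5.1% at r = 1 and 9.5% at r = 1.5. This is closer to 5% than the pooled test at the two unequal ratios, but not at it.

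**Step 4: both changes together.** Welch's test on cohort against non-cohort patients gives 4.96% to 5.04% at every size and ratio tried.

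**The case against.** The strongest reply is that 10.5 is descriptive. It names no test, section 2.3 states no hypotheses, the main analysis is a Kaplan-Meier estimate, and no endpoint or decision rests on a p-value for age or BMI. This stands, and it limits the consequence. It does not remove the point, because 10.5 goes on to announce a comparison and 10.2 is the only rule that says how continuous variables are tested.

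A second reply is that 10.4 already handles unequal variances through the non-parametric fallback. This stands in part: the fallback reduces the distortion (9.5% against 15.4% at r = 1.5) without removing it, and it does nothing for the overlap.

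A third reply is that very unequal group sizes and different spreads are both assumed. That is correct. At 20 v 20 the pooled test stays between 5.0% and 5.2% over r = 0.5 to 2, and the direction of error depends on which group is more variable. A frame much larger than the cohort is likely, since it covers all the surgeon's total hip replacements in the period, but the documents do not give its size.

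A reader might infer that the plan's only protection against selection is invalid. The documents do not support that. Section 4.1 also lists consecutive recruitment, sections 5 and 6.1 have the clinical research associate confirm that the cohort is complete and consecutive, and two of the four characteristics in 10.5 are categorical and untouched by the t-test issue.

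**Conclusion.** The point holds as a minor one. The overlap follows from the definition in 10.5 and needs no assumption about spread: it makes an independent-samples test conservative, by an amount that depends on frame size (2.9% at 20 in 200, 3.8% at 20 in 400, equal SDs). The unequal-variance effect is conditional. If the frame is several times larger than the cohort and the SDs differ, the pooled test's error rate moves well away from 5% (about 0.8% to 15.4% at 20 v 180 for SD ratios 0.67 and 1.5). It would be too strong to say that the plan prescribes an equal-variance test for this comparison, since that is inferred from 10.2. Nor would replacing Student's test by Welch's suffice while the groups overlap. The survival estimate and the within-patient score comparisons are unaffected.

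**What to change.** Amend 10.5 in two respects.

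1. Define the comparison as cohort patients against the patients of the frame who are not in the cohort. The full frame can still be described as planned.
2. For age and BMI, name Welch's unequal-variance t-test and report the mean difference with its 95% interval. Put the interval first, since size of difference is what a reader needs to judge representativeness.

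A cross-reference in 10.2 would make clear that Student's test there does not govern this between-group comparison. The cost is a sentence or two and, in the analysis, a standard option. The one practical requirement is that cohort patients can be identified in the anonymised frame list. The prosthesis type that 10.5 already lists should largely allow this, and a cohort flag would settle it. No new data are needed from patients.
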